6.4.3. Supplemental Analyses of Primary Efficacy Endpoint

6.4.3.1. Per Protocol Set

The main analysis described in Section 6.4.1 will be repeated using the PP set to investigate the impact of changing the population in the estimand. Missing data (regardless of the reason being the ICEs or not) will be handled implicitly within the MMRM analysis under the assumption of missing at random (MAR).

6.4.3.2. Slope Analysis

The mean rate of change (ie, slope) in observed log-transformed uPCR values will be compared between treatment groups using the linear mixed effects model for slope analysis of continuous outcomes described above in Section 6.1. The mean rate of change (slope), standard errors, and confidence interval will be estimated for the baseline to week 26 period for each treatment group. In addition, the estimated difference in slopes between the treatment groups along with the 95% CIs and p-value will be reported. Strategies for addressing ICEs are the same as the ones described in Section 6.4.1.

6.4.4. Subgroup Analyses of Primary Efficacy Endpoint

Subgroup analyses will be performed to evaluate the consistency of the primary analysis results across subgroups defined by demographic and baseline characteristics. Analyses will be performed for the primary efficacy endpoint for each of the following subgroups (as appropriate per actual subgroup sample size, levels with low sample size may be pooled to allow for an analysis to be conducted):

- Age group: adolescent, adult
- Sex: male, female
- Race: Caucasian, non-Caucasian
- Geographic region: United States, Rest of World
- Disease type: C3G, IC-MPGN
- Transplant history: nontransplant, posttransplant
- Baseline FMU uPCR: <3000 mg/g, ≥3000 mg/g
- Baseline eGFR: <60 mL/min/1.73 m², >60 mL/min/1.73 m²
- Baseline C3 level: normal, below the LLN
- Baseline immunosuppressants use: yes, no (based on ATC level 2 of "IMMUNOSUPPRESSANTS" and/or "CORTICOSTEROIDS FOR SYSTEMIC USE")

The estimated treatment effects and corresponding 95% CIs and p-values from the models will be displayed graphically for each level of the subgroups specified via forest plots.

6.5. Analyses of Key Secondary Efficacy Endpoints

The following subsections describe the analyses of the key secondary efficacy endpoints of the study. All analyses of the key secondary efficacy endpoints will be done primarily using the ITT set.

6.5.1. The Proportion of Participants Who Meet the Criteria for Achieving a Composite Renal Endpoint

The key secondary efficacy endpoint of the proportion of participants who meet the criteria for achieving a composite renal endpoint at week 26 will be examined with the following null $(H_{2,0})$ and alternative $(H_{2,1})$ hypotheses:

- H_{2,0}: There is no difference in proportion of participants who meet the criteria for achieving a composite renal endpoint at week 26 between the pegcetacoplan and placebo treatment groups.
- H_{2,1}: There is a difference in proportion of participants who meet the criteria for achieving a composite renal endpoint at week 26 between the pegcetacoplan and placebo treatment groups.

A participant meets the requirements of the composite renal endpoint if they satisfy:

- (1) A stable or improved eGFR compared to baseline (≤15% reduction in eGFR), and
- (2) A \geq 50% reduction in uPCR compared to baseline.

For requirement (1), the eGFR status at week 26 will be calculated using the following steps:

- 1. Baseline eGFR value will be calculated using the last non-missing assessment prior to first dose.
- 2. Week 26 eGFR value will be calculated based on the week 26 assessment result.
- 3. Each participant will be categorized as either a "stable or improved" or not "stable or improved" according to whether the change from baseline in eGFR calculated from steps 1 and 2 is a reduction of no more than 15%.

For requirement (2), the uPCR response status at week 26 will be calculated using the following steps:

- 1. Baseline uPCR value will be calculated as the average of the uPCR measurements from at least 6 of the 9 FMU samples collected between the start of screening and day 1, inclusive.
- 2. Week 26 uPCR value will be calculated as the average of the uPCR measurements from at least 6 of the 9 FMU samples collected in week 24, week 25, and week 26.
- 3. Each participant will be categorized as either a success or a failure according to whether the change from baseline in uPCR calculated from steps 1 and 2 is a reduction of at least 50%.

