12.1. Determination of Sample Size

Approximately 80 to 100 participants, including patients with native kidney disease or post-transplant, will be randomized 1:1 to pegcetacoplan or placebo with 40 to 50 participants per arm.

Based on preliminary data from Study APL2-201, a reduction of 60% in uPCR in the pegcetacoplan group at week 26 is assumed vs a reduction of 20% in uPCR in the placebo arm, which corresponds to mean log ratio to baseline of -0.92 vs -0.22 respectively, and a standard deviation of 0.88 (on log-scale). Based on this assumption, a sample size of 70 participants in total provides at least 90% power at 1-sided significance level of 0.025. Considering a 10% attrition to account for potential missing assessments and impact by COVID-19, it is expected that at least 78 participants with native kidney disease should be enrolled.

A minimum of 63 participants with C3G in native kidneys will be enrolled, which is approximately 80% of the enrolled participants with native kidney disease.

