6. EFFICACY ANALYSES

Efficacy analysis including primary, key secondary, additional secondary, and exploratory analysis will be performed primarily using the ITT set, with participants grouped according to the treatment assigned at randomization. Available data from all randomized participants regardless of adherence to the protocol will be included in the efficacy analysis, this includes data from participants who discontinued study drug early but continued with study assessments. All efficacy data will be listed for the ITT set.

All statistical tests will be performed at 2-sided 5% level of significance and all confidence intervals will be two-sided 95% confidence intervals.

Unless otherwise noted, the following randomization stratification factors will be adjusted for in analysis of efficacy endpoints in the overall population:

- Participants with posttransplant recurrence versus nontransplant participants
- Participants with baseline renal biopsies versus participants without baseline renal biopsies

If participants are found to have had the incorrect stratum assigned at randomization, they will be analyzed according to the randomization stratum.

For potential treatment imbalance, will check imbalance between treatment and placebo. In case there are major imbalances on important prognostic factors other than those already included in the analysis model, additional sensitivity analyses may be performed to adjust any or all of these factors if appropriate. Data will be verified for outliers. Sensitivity analyses may be performed using more robust approaches or excluding outliers.

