6.6.2. The Proportion of Participants With Normalization of Serum Albumin Levels

For participants with serum albumin levels below LLN at baseline, the additional secondary efficacy endpoint of the proportion of participants with normalization of serum albumin levels at week 26 will be examined with the following null (H_{8,0}) and alternative (H_{8,1}) hypotheses:

- H_{8,0}: There is no difference in proportion of participants who achieve normalization of serum albumin levels at week 26 between the pegcetacoplan and placebo treatment groups.
- H_{8,1}: There is a difference in proportion of participants who achieve normalization of serum albumin levels at week 26 between the pegcetacoplan and placebo treatment groups.

The serum albumin levels status at week 26 will be calculated using the following steps:

- 1. Baseline serum albumin value will be calculated as the average of up to 2 serum albumin measurements preceding and including day 1. Participants will be included in the denominator of this calculation only if the baseline albumin value is below the LLN.
- 2. Week 26 serum albumin values will be calculated as the average of up to 2 serum albumin measurements preceding and including week 26, no earlier than week 20 measurement.

3. Each participant will be categorized as either a success or a failure according to whether the week 26 serum albumin values as calculated in Step 2. Values greater than or equal to the LLN will be categorized as a success; values less than the LLN will be categorized as a failure.

The additional secondary endpoint will be analyzed in the ITT set with participants grouped according to the treatment assigned at randomization.

A logistic model will be used to analyze the additional secondary endpoint. The model will include treatment group as the independent variable and adjusted for baseline albumin value, disease type (C3G vs IC-MPGN), and stratification factors. Further details on the presentation of the results are described in Section 6.1. Strategies for addressing ICEs are the same as the ones described in Section 6.5.1.1.

For participants with serum albumin levels below the LLN at baseline, the numbers and proportion of participants with normalization of serum albumin levels at week 26 will be tabulated by treatment group. The observed values for serum albumin will be summarized by treatment group and visit.

All serum albumin data will be listed for the ITT set.

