13.3. Definition of Baseline, RCP, and OLP

For all evaluations unless otherwise noted, baseline is defined as the most recent non-missing measurement prior to the first administration of study drug. Baseline can be the same date as first dose, given the measurement is expected prior to first dose when only date information is available.

In by-visit summary tables, the baseline will be summarized using all available data, but also for each visit using only the baseline data from participants with available data at the visit; hence the mean change from baseline will equal the mean visit value – mean baseline value.

Throughout this document 'change from baseline' refers to the actual change from baseline (ie, visit value – baseline value).

The date when a participant receives first administration of OLP drug will be defined as the start date of the participant's OLP, and that date minus one day will be the end date of the participant's RCP.

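### Both key secondary endpoints involving eGFR use one value at each end, although repeat values are already collected; averaging two would cut misclassification at the 15% limit and recover some precision

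*SAP*

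**What the plan says.** **Composite renal endpoint (SAP 6.5.1).** At the start, "Baseline eGFR value will be calculated using the last non-missing assessment prior to first dose". At the end, "Week 26 eGFR value will be calculated based on the week 26 assessment result". A fall of no more than 15% between these two values counts as stable or improved.

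**Change in eGFR (SAP 6.5.5).** No specific baseline is given, so the general rule in SAP 13.3 applies: "baseline is defined as the most recent non-missing measurement prior to the first administration of study drug". SAP Table 1 sets the target as the change to week 26.

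**What is collected.** The schedule of activities (Protocol Table 2, SAP 17.1) has eGFR at both screening visits, day 1, week 24 and week 26. The table's ordering note puts blood sampling before dosing, so day 1 counts as pre-dose. That makes three values before treatment and two at the end.

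**What is done for other markers.** uPCR averages at least 6 of 9 samples at each end, and the primary contrast averages weeks 24, 25 and 26 (SAP 6.4.1, 6.5.1). For albumin, "Baseline serum albumin value will be calculated as the average of up to 2 serum albumin measurements preceding and including day 1", with a matching rule at week 26. Serum C3 is treated the same way (SAP 6.6.2, 6.6.3).

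**The concern.** The effect on eGFR is the first secondary objective, yet the eGFR endpoints carry more measurement noise than the schedule requires. A difference of two single creatinine-based values carries the within-person error twice. Around a fixed 15% limit, that error fails some participants whose kidney function has not changed and passes some whose function has truly fallen.

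The composite is the first test after the primary endpoint in a fixed sequence that stops at the first non-rejection (SAP 6.2), so lost power there affects everything below it. Change in eGFR is the last key secondary, and the protocol's summary of changes says histologic changes are expected before eGFR improves. A small expected effect makes avoidable noise more costly.

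**Working it through.** **1. The plan's own figure.** The only power statement concerns uPCR: "a sample size of 70 participants in total provides at least 90% power at 1-sided significance level of 0.025". The inputs are mean log ratios of −0.92 and −0.22 (difference 0.70) and SD 0.88. Per arm, 2 × (0.88 × (1.960 + 1.282) / 0.70)² = 33.2, so 34 per arm or 68 in total. With the t distribution, power is 89.8% at 34 per arm and 90.7% at 35, which gives 70. Dividing by 0.9 for attrition gives 78. The figure reproduces and this point does not affect it. No power or variability is stated for eGFR, so the within-person CV below is an assumption, shown over a range.

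**2. Classification at the 15% limit.** On the log scale, s = √ln(1 + CV²), which is 0.0500, 0.0699 and 0.0998 at CV 5%, 7% and 10%. The limit is ln 0.85 = −0.1625. The SD of the log ratio is s√2 with single values. With two values averaged at each end it is s if errors are independent, and s√1.4 if the two values at each end correlate at 0.4.

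| CV | Stable participant fails: single | Averaged | Averaged, correlation 0.4 | True 20% fall passes: single | Averaged |
|---|---|---|---|---|---|
| 5% | Φ(−2.300) = 1.1% | Φ(−3.252) = 0.1% | 0.3% | 19.5% | 11.3% |
| 7% | Φ(−1.644) = 5.0% | Φ(−2.325) = 1.0% | 2.5% | 27.0% | 19.3% |
| 10% | Φ(−1.152) = 12.5% | Φ(−1.629) = 5.2% | 8.4% | 33.4% | 27.2% |

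The passing probabilities are 1 − Φ((ln 0.85 − ln 0.80)/SD). Both kinds of error shrink.

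**3. Composite power.** The design assumptions imply uPCR responder rates of Φ((ln 0.5 + 0.92)/0.88) = 60.2% and Φ((ln 0.5 + 0.22)/0.88) = 29.5%. Assume that every uPCR responder is truly stable and that eGFR error is unrelated to uPCR. Each rate is then multiplied by one minus the false-failure probability. At CV 7% with single values this gives 57.2% against 28.1%, and with averaging 59.6% against 29.2%. Power is for a two-sided 5% comparison of two proportions, normal approximation. The 62 per arm is half of the 124 enrolled, assuming an even split; 39 per arm is half of the planned 78.

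| CV | 62 per arm: single | Averaged | Averaged, correlation 0.4 | 39 per arm: single | Averaged |
|---|---|---|---|---|---|
| 5% | 93.4% | 93.9% | 93.8% | 77.9% | 78.7% |
| 7% | 91.6% | 93.4% | 92.8% | 74.8% | 78.0% |
| 10% | 87.3% | 91.5% | 89.7% | 68.6% | 74.7% |

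At 62 per arm the gain is about 0.4, 1.9 and 4.2 points, or 0.3, 1.2 and 2.4 points with the correlation.

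**4. Change in eGFR.** Let τ be the between-person SD, δ the SD of true 26-week change and w the within-person SD, with n_b and n_f values averaged at baseline and at the end. The baseline-adjusted residual variance is δ² + w²/n_f + τ² − τ⁴/(τ² + w²/n_b). All three SDs are assumptions, in mL/min/1.73 m². With τ = 25, δ = 10 and w = 5, single values give 100 + 25 + 24.0 = 149.0. Two at each end give 100 + 12.5 + 12.3 = 124.8, a fall of 16%. Over w from 4 to 6 and τ from 25 to 30, with independent errors:

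| δ | Fall in residual variance | Fall in standard error |
|---|---|---|
| 6 | 23% to 33% | 12% to 18% |
| 10 | 12% to 20% | 6% to 11% |
| 15 | 6% to 12% | 3% to 6% |

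**The case against.** - **Consistency.** The last pre-dose value is the SAP's general baseline rule and nothing contradicts it. That stands: this is a choice that could be improved, not an error. A reader might infer from the protocol's reference to the baseline visit that only one value is allowed. The same phrase covers uPCR, whose baseline spans screening to day 1, so the wording neither forbids averaging nor makes single values wrong.
- **Regulatory origin.** Protocol Appendix 1 records that the criterion for stable eGFR was redefined at FDA suggestion. The recorded change concerns the criterion and the composite, and says nothing on how many values to use.
- **Other analyses use more data.** The eGFR MMRM includes every visit, the slope analysis (SAP 6.5.5.3.2) uses all of them, and SAP 6.7.2 adds up to three years of history. With complete data and an unstructured covariance, however, the week 26 contrast gains little from week 24, and the baseline covariate is still one value. The slope analyses are supplemental or exploratory and do not replace the two tests in the sequence. The planned breakdown of the composite by component shows who failed on eGFR, but not why.
- **Side effects of averaging.** Copying the albumin rule, which reaches back to week 20, would let a participant without a week 26 eGFR pass, against the non-responder rule in SAP 6.5.1.1. This is right, and the fix avoids it. Participants may also be held in screening, so the older baseline value can be more than two weeks old. In progressive disease that tends to raise the baseline slightly.
- **Timing.** SAP Addendum section 11 says that week 26 results were reported in a study report dated 05 December 2024. Replacing the tested definition afterwards would be a post hoc change. This stands too.

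**Conclusion.** The point holds as an inexpensive improvement to two key secondary endpoints. The collection schedule and the single-value rules are plain in the documents. The size is not, because it depends on an assumed within-person CV. At 5% the effect on the composite is negligible. At 7% to 10% it is worth about 2 to 4 points of power at 62 per arm with independent errors, and about 1 to 2.5 points at a correlation of 0.4. For change in eGFR, the 6% to 33% fall in residual variance depends mainly on how much true change varies between participants. The top of that range, equivalent to about 49% more participants, pairs the largest assumed noise with the smallest assumed true variation and should not be read as typical.

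A reader might infer that the composite result is biased or its type I error inflated. The documents do not support that. The same rule applies to both arms, and noise passes true decliners as well as failing stable participants, so the consequence is a diluted contrast.

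**What to change.** - **SAP 6.5.1.** Define baseline eGFR as the average of up to 2 values preceding and including day 1, and week 26 eGFR as the average of the week 24 and week 26 values (week 26 alone if week 24 is missing). Keep the SAP 6.5.1.1 rule that a missing week 26 eGFR is a non-response.
- **SAP 6.5.5.** Use the same baseline, and make the MMRM contrast the equal-weighted average of weeks 24 and 26.
- **Sensitivity.** Keep the single-value version of both endpoints as a sensitivity analysis.
- **Where the week 26 analysis is already reported.** Leave the prespecified definition in the testing sequence unchanged, and report the averaged-eGFR version as a clearly labelled sensitivity analysis. None is planned at present.

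**Cost.** SAP wording and derivation code only, with no new samples or visits. The downside is that baseline reaches back to screening visit 2 or earlier, and the endpoint describes weeks 24 to 26 rather than one visit, as the plan already accepts for uPCR.

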6.5.1.1. Main Analysis

The key secondary endpoint will be analyzed in the ITT set with participants grouped according to the treatment assigned at randomization.

A logistic model will be used to analyze the key secondary endpoint. The model will include treatment group as the independent variable and adjusted for baseline eGFR values, baseline log-transformed uPCR values, disease type (C3G vs IC-MPGN), and stratification factors. Further details on the presentation of the results are described in Section 6.1.

A composite strategy will be used for addressing the ICEs listed in Table 1. In the composite strategy, the composite renal endpoint status at or after the occurrence of any of these ICEs will be regarded as non-responder. Additionally, participants with missing eGFR and/or uPCR values at week 26 for reasons other than those listed as ICEs will be regarded as non-responder.

The numbers and proportion of participants who meet the criteria for achieving a composite renal endpoint at week 26 will be tabulated by treatment group, including detailed breakdown on each of the two requirements.

All composite renal endpoint achievement data will be listed for the ITT set.

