6.1. Analysis Models

In general, data will be analyzed using the approaches described below.

Mixed-effect model for repeated measures (MMRM) for continuous outcomes

Longitudinal assessments for changes from baseline in continuous outcomes will be analyzed using a mixed-effect model for repeated measures (MMRM). The model will include fixed categorical effects for treatment group, visit, disease type (C3G vs. IC-MPGN), baseline immunosuppressants use (yes vs. no, to add this effect for primary endpoint analysis only), stratification factors, and the visit-by-treatment group interaction, as well as the continuous, fixed covariate of the baseline value of the endpoint. The least square (LS) means with standard errors (SEs) and 95% confidence intervals (CIs) of the change from baseline will be presented by treatment group and visit; between-treatment differences and 95% CIs and p-values will be presented by visit. LS means (±SE) will be plotted over time by treatment group.

A common unstructured covariance matrix will be used. If the model fails to converge, the following covariance structures will be fit in this order until convergence is met: (*i*) heterogenous autoregressive ARH(1), (*ii*) autoregressive AR(1), (*iii*) compound symmetry CS. The sandwich estimator (Diggle et al. 1994) will be used to estimate the standard errors of the fixed effects parameters.

Logistic regression model for binary outcomes

Binary outcomes will be analyzed using a logistic regression model. The model will include treatment group as independent variable and adjusted for baseline value of the variable(s) used to define the endpoint, disease type, and stratification factors. Point estimates for proportions and difference in proportions will be presented. The p-value and odds ratio of being a responder for the pegcetacoplan group to being a responder for the placebo group with associated 95% CI will be provided. In situations where event rates are low leading to convergence issue for the logistic regression model, alternative methods such as removal of covariates may be considered when appropriate.

Analysis of covariance (ANCOVA)

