6.3. Estimands

The primary objective of this study is to assess the efficacy of twice-weekly SC doses of pegcetacoplan compared with that of placebo in patients with primary C3G or IC-MPGN on the basis of a reduction in proteinuria.

The estimands and their attributes for the primary and all comparative key secondary and additional secondary endpoints are shown in Table 1 below. This includes strategies for addressing the following intercurrent events (ICEs):

- ProhibiRescue = use of prohibited concomitant medication specified in Protocol Section 8.3.3, or use of rescue therapies defined in Protocol Section 8.3.2
- RenalReplace = start renal replacement therapy (dialysis and/or renal transplant)
- DisctTrt = permanent discontinuation of study treatment

Table 1: Estimands and Attributes for Primary, Key Secondary, and Additional Secondary Endpoints

Socona	Secondary Endpoints				
For all estimands: A. Population: participants with C3G or IC-MPGN defined through the study inclusion/exclusion criteria in the ITT Set B. Treatment regimens of interest: • Twice-weekly SC doses of pegcetacoplan for 26 weeks of treatment • Twice-weekly SC doses of placebo for 26 weeks of treatment					
C: Variable (or endpoint) D: Strategies for addressing ICEs (event†: strategy‡) E: Population-level sum					
Primary Estimand					
Log-transformed ratio of uPCR at week 26 compared to baseline	ProhibiRescue: hypothetical strategy RenalReplace: hypothetical strategy DisctTrt: treatment policy strategy	Difference in mean change of log-transformed uPCR from baseline to week 26 (measured by equal-weighted average over weeks 24, 25, and 26) between the pegcetacoplan group and the placebo group.			
Key Secondary Estimands	(for comparative endpoints)				
The proportion of participants who meet the criteria for achieving a composite renal endpoint at week 26	ProhibiRescue, RenalReplace, DisctTrt: composite strategy	Odds ratio of achieving a composite renal endpoint for the pegcetacoplan group to achieving a composite renal endpoint for the placebo group at week 26.			
The proportion of participants with a reduction of at least 50% from baseline in uPCR at week 26	ProhibiRescue, RenalReplace, DisctTrt: composite strategy	Odds ratio of achieving a reduction of at least 50% from baseline in uPCR for the pegcetacoplan group to achieving a reduction of at least 50% from baseline in uPCR for the placebo group at week 26.			

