17.2.4. Logistic Model

```
* logistic regression, take example of FMU uPCR of at least 50% reduction
from baseline
*_____
* first select out the binary variable of the endpoint (avalc)
data upcr50;
set ADAM.ADEFF;
if paramcd = 'UPRTRD50';
if ittfl='Y';
 if avisit = 'Week 26';
if an101fl='Y';
keep subjid trt01p aval avalc param paramcd stragr1 stragr2p
disesbio;
run:
* then obtain the baseline variable (log-transformation) FMU uPCR value
data fmuupcr;
set adam.adeff;
if paramcd='LNUPRCRF';
 if ittfl='Y';
 if basetype='NORMAL';
if avisit='Baseline';
 logbase = aval;
keep subjid logbase;
run;
* then merge together to obtain all necessary variables
data upcr50;
merge upcr50 fmuupcr;
by subjid;
run;
proc sort data=upcr50; by trt01p;run;
** Descriptive summary of the data;
proc freq data=upcr50;
 by trt01p;
 tables avalc/nocol nopercent nocum;
run;
** logistic regression that produces Proportion (SE), CI, odd ratio
and CI, and p-value;
proc logistic data=upcr50;
class trt01p(ref='Placebo') stragr1 stragr2p disesbio/param=glm;
model avalc(event='Y') = trt01p logbase stragr1 stragr2p disesbio /
clodds=wald orpvalue;
oddsratio trt01p;
```

```
lsmeans trt01p / ilink e cl;
store LogFit;
ods output coef=Coeffs;
run;
```

** calling macro to produce difference in proportion and CI of it; %*NLMeans*(instore=LogFit, coef=Coeffs, link=logit, title=Differences of Proportion)

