17.2.5. ANCOVA Model

```
* Read Analysis data
*_____
* Example used here is the key secondary endpoint of activity score of the
C3G Histologic Index at Week 26.
* Note the main analysis should be performed based on multiple imputation
dataset with ICE addressed (see sample code under 1.2.2), here is only an
illustration of the key code using data without the multiple imputation.
*----;
data activity;
set ADAM.ADMI;
if paramcd = 'C3HISACT';
 if ittfl='Y';
 if avisit = 'Week 26';
if anl01fl='Y';
keep usubjid trt01p chg base stragr1 stragr2p disesbio;
run;
proc mixed data=activity;
by <subgroup>; *note: to add this line if for subgroup analysis;
class trt01p disesbio stragr1 stragr2p;
model chg = trt01p base disesbio stragr1 stragr2p;
lsmeans trt01p /om cl pdiff;
run;
17.2.6.
       Time-to-Event Analysis
```

```
proc lifetest data=adtte;
time aval*cnsr(1);
strata stragr1 stragr2p disesbio / group=trt01p;
run;
proc phreg data=adtte;
 class trt01p/ param=reference ref=last;
model aval*cnsr(1) = trt01p loguPCR BL eGFR BL/rl ties=efron;
strata stragr1 stragr2p disesbio;
run;
```

STATISTICAL ANALYSIS PLAN (FINAL)

Statistical Analysis Plan: 2.0 Protocol Number: APL2-C3G-310

STATISTICAL ANALYSIS PLAN FOR CLINICAL STUDY REPORT ADDENDUM

Pegcetacoplan (APL-2) PHASE 3

A Phase 3, Randomized, Placebo-Controlled, Double-Blinded, Multicenter Study to Evaluate the Efficacy and Safety of Pegcetacoplan in Patients with C3 Glomerulopathy or Immune-Complex Membranoproliferative Glomerulonephritis

PROTOCOL IDENTIFIER: VALIANT

Study Sponsor(s): Apellis Pharmaceuticals, Inc [name]

Author: PPD

Protocol: Amendment 4 dated 25 April 2024

SAP Version #: 2.0

SAP Date: 10 February 2025

Status: Final

Individuals printing or viewing Apellis procedural document from a source other than the Electronic Document Management System are responsible for ensuring that they are printing or viewing the current version.

This document may not be distributed outside of Apellis without approval from Global Quality.

REVISION HISTORY

Version	Issue Date	Summary of Changes	
1.0	27 June 2024	New document to describe the primary analysis (Week 26) CSR addendum analyses	
2.0	10 February 2025	This update describes the analyses for the final database lock with all available Week 52 data. Please refer to Version 1.0 for analyses related to the primary (Week 26) analyses.	
		Updated to remove Week 52 Set and replace with ITT Set.	

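### The adjusted response proportions and their difference for binary endpoints have no stated estimator, and the only code given evaluates them at equal covariate weights rather than over the analysed participants; separately, the odds ratio in SAP Table 1 is not labelled conditional or marginal.

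*SAP*

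**What the plan says.** - **Model.** SAP 6.5.1.1 analyses the composite renal endpoint by logistic regression, "adjusted for baseline eGFR values, baseline log-transformed uPCR values, disease type (C3G vs IC-MPGN), and stratification factors". SAP 6.5.2.1 does the same for 50% uPCR response, without baseline eGFR.
- **Estimand.** In SAP 6.3, Table 1, the population-level summary for the composite is "Odds ratio of achieving a composite renal endpoint for the pegcetacoplan group to achieving a composite renal endpoint for the placebo group at week 26". It does not say conditional or marginal, and it lists no difference in proportions.
- **Extra effect measure.** SAP 6.1 states for binary outcomes: "Point estimates for proportions and difference in proportions will be presented". No estimator or weighting is named.
- **Code.** SAP 17.2.4 uses 50% uPCR response as its example. It declares "class trt01p(ref='Placebo') stragr1 stragr2p disesbio/param=glm" and fits "model avalc(event='Y') = trt01p logbase stragr1 stragr2p disesbio", with no treatment interaction. It then requests "lsmeans trt01p / ilink e cl" and passes the stored coefficients to the NLMeans macro for the difference.
- **Contrast.** The ANCOVA code in SAP 17.2.5 has "lsmeans trt01p /om cl pdiff", and the MMRM code in 17.2.1 also uses the observed-margins option. Only the logistic code omits it, and no reason is given.

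**The concern.** Without OM, LSMEANS weights the levels of each CLASS factor equally. The adjusted proportions are then for a mix that is half post-transplant, half without a baseline biopsy and half IC-MPGN, with continuous covariates at their mean. The planned trial is different. SAP 3.1 allows up to 22 post-transplant participants out of 80 to 100, and SAP 3.4 puts C3G at about 80% of native-kidney participants. Only adolescents may lack a baseline biopsy.

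A second problem is separate from the weights. The code averages the linear predictor first and applies the inverse link afterwards, which is not the average of the predicted probabilities.

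The same report would then carry crude proportions by arm next to adjusted proportions that refer to nobody enrolled, with no text to explain the gap. The template serves the composite, 50% uPCR response, proteinuria below 1 g/day, albumin and C3 endpoints, and C3c staining with a different covariate set.

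The odds ratio raises a different question. A covariate-adjusted odds ratio is conditional, and it differs from the marginal one whenever covariates are prognostic. SAP 6.1 also lets covariates be removed if the model does not converge. A conditional odds ratio changes meaning with its covariate set; a standardised difference does not.

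**Working it through.** **1. The plan's own figure.** No power or response rate is given for the binary endpoints. For the primary endpoint (SAP 3.4: means -0.92 vs -0.22, SD 0.88):
- n per arm = 2 × (1.960 + 1.282)² × 0.88² / 0.70² = 33.2, so 34 per arm, 68 in total.
- With 35 per arm, power = Φ(0.70 / (0.88 × √(2/35)) - 1.96) = Φ(1.37) = 91.4%.
- 70 / 0.9 = 77.8, so 78.

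The stated 70, at least 90% and 78 reproduce.

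**2. Implied 50% uPCR response rates**, assuming normality on the log scale:
- Pegcetacoplan: Φ((ln 0.5 + 0.92) / 0.88) = Φ(0.258) = 0.602.
- Placebo: Φ((ln 0.5 + 0.22) / 0.88) = Φ(-0.538) = 0.295.
- Marginal difference 0.306. Marginal OR = (0.602/0.398) / (0.295/0.705) = 3.60.

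**3. Quantities compared.** Take logit p = α + θ·arm + b₁·transplant + b₂·no biopsy + b₃·IC-MPGN + g·x, with x one standardised continuous covariate.
- Conditional OR: exp(θ).
- Code as written: expit(α + θ·arm + ½(b₁ + b₂ + b₃)), differenced between arms.
- With OM: the same, with each ½ replaced by the observed share.
- Standardised: expit of each participant's own predictor under each arm, then averaged.

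The weighting term is the same in both arms, so it cancels from the odds ratio. It does not cancel from the difference in proportions.

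**4. Size under assumed inputs.** Assumed shares: transplant 10-22%, no biopsy 10-40%, IC-MPGN 20%. The upper transplant share and the IC-MPGN share follow SAP 3.1 and 3.4; the biopsy share is not in the documents. The covariate effects (log odds, x per SD) are also assumed. Intercepts are solved so that the standardised rates equal 0.602 and 0.295 in every row; the marginal difference is therefore always 0.306.

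| Shares % (transplant / no biopsy / IC-MPGN) | b₁, b₂, b₃, g | Conditional OR | Code: arm proportions | Code: difference | OM difference |
|---|---|---|---|---|---|
| any | 0, 0, 0, 0 | 3.60 | 0.602 vs 0.295 | 0.306 | 0.306 |
| 10 / 10 / 20 | -1, -1, -1, -0.5 | 4.21 | 0.344 vs 0.110 | 0.233 | 0.339 |
| 10 / 10 / 20 | 1, 1, 1, -0.5 | 4.25 | 0.829 vs 0.533 | 0.296 | 0.342 |
| 22 / 10 / 20 | -1, 1, -1, -0.5 | 4.31 | 0.571 vs 0.236 | 0.335 | 0.345 |
| 10 / 40 / 20 | -1, -1, -1, -1 | 5.20 | 0.432 vs 0.127 | 0.304 | 0.383 |
| any | 0, 0, 0, -1 | 4.68 | 0.622 vs 0.260 | 0.362 | 0.362 |
| 10 / 40 / 20 | 1, 1, 0, -1 | 5.05 | 0.736 vs 0.356 | 0.380 | 0.378 |

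Differences are taken before rounding. Second row by hand: the solved intercepts are 0.852 and -0.586, and the equal-weight shift is -1.5. This gives expit(-0.648) = 0.344 and expit(-2.086) = 0.110. The OM shift is -0.1 - 0.1 - 0.2 = -0.4, giving expit(0.452) - expit(-0.986) = 0.611 - 0.272 = 0.339. The sixth row isolates the inverse-link problem: with no factor effects the weights are irrelevant, and the difference is still 0.362.

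**5. Check on a fitted model.** 200,000 simulated participants, shares 10 / 15 / 20%, logit p = -0.6 + 1.45·arm - 1·transplant + 0·no biopsy - 0.8·IC-MPGN - 0.6·x.
- Equal weights: expit(-0.05) - expit(-1.5) = 0.305.
- OM: expit(0.59) - expit(-0.86) = 0.346.
- Standardised 0.313; crude 0.313.
- Fitted odds ratio 4.267 under both weightings; marginal OR 3.66.

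**The case against.** The strongest reply is that SAP 17.2 labels its code as examples that may need changes to match the SAP text, and no SAP text prescribes equal weights. The difference in proportions is a presentation item outside the test sequence. Crude numbers and proportions are tabulated by arm for these endpoints, so the enrolled population is not hidden. In the fitted check the existing code (0.305) was closer to the standardised 0.313 than OM was (0.346).

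Most of this stands as a limit on the point. It does not remove it, because Section 6.1 is silent and a programmer has only the code to follow.

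Several stronger readings are tempting but unsupported:
- **That equal weighting distorts the odds ratio.** It cancels in a main-effects model.
- **That Table 1 is contradicted.** It lists no difference in proportions, and its odds ratio is unlabelled rather than stated to be marginal. The protocol and SAP consistently describe an odds ratio from an adjusted model.
- **That the benefit is systematically understated.** The table shows errors both ways.
- **That C3c proportions assume half the participants lack a biopsy.** That analysis is in adults with evaluable biopsies, so the biopsy factor should have one level.

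**Conclusion.** The point holds for the adjusted proportions and their difference. Followed as written, the code gives figures that are not those of the analysed population. In the examples the difference runs from about 0.23 to 0.38 against a marginal 0.31, and single-arm proportions move further. These are illustrations, not bounds. They rest on assumed covariate effects and an assumed biopsy share, and with no covariate effects the discrepancy is zero.

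For the odds ratio the finding is narrower: a missing label. In the examples with prognostic covariates the conditional ratio is 4.2 to 5.2 where the marginal one is 3.60.

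Only the reported effect size is at issue. In this model a null conditional odds ratio implies a null marginal one, so the P values, the testing order and type I error do not change.

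**What to change.** Keep the logistic model and its test. In SAP 6.1 and 17.2.4, replace the LSMEANS and NLMeans step with standardisation:
1. Predict each participant in the analysed set under both arms from the fitted model.
2. Average the predictions by arm. Report the two proportions and their difference with a delta-method or bootstrap CI.
3. Name the analysed set: the ITT set in general, adults with evaluable biopsies for C3c, and participants below the LLN at baseline for albumin and C3.

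In Table 1, label the odds ratio as conditional on the listed covariates. The standardised marginal odds ratio can be added from the same predictions.

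Do not just add OM. It still applies the inverse link to an averaged linear predictor and gave 0.34 to 0.38 against 0.31 in the rows with covariate effects.

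The cost is a few lines of code and two or three sentences of text, with no change to data collection, alpha or the hierarchy. If the marginal odds ratio is added, expect it to look smaller than the model one.
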